## 10 STATISTICAL METHODS

### 10.1 GENERAL PRINCIPLES

All variables will be presented descriptively.

All statistical methods will be based on the International Conference on Harmonisation (ICH) E9 document “Statistical Principles for Clinical Trials”.

Data will be summarised by treatment group (50mg ABX464 (101 study) + 50mg ABX464 (102 extension) and Placebo (101 study) + 50mg ABX464 (102 extension)). A total column showing all patients will be included for baseline, safety and efficacy summaries. Where appropriate, data will also be summarised by visit with summaries for each visit attended as scheduled and an additional summary for final (last scheduled visit or early withdrawal). The format of the summaries is defined in the shells at the end of this document.

In safety tables of continuous variables, standard descriptive statistics (Sample number n, mean, Standard Deviation (SD), Standard Error of the Mean (SEM), median, minimum and maximum) will be presented. In summary tables of continuous variables, standard descriptive statistics (n, mean, 95% confidence interval [CI], SD, median, minimum and maximum and quartiles) will be presented. The minimum and maximum statistics will be presented in summary tables to the same number of significant figures as the original data. The mean, median, SD and SEM will be presented to one more significant than the original data.

- For numeric data which includes non-numeric values (e.g. lab results reported as < 10 or >100) the following principles will be applied when summarising the data:
  - Below Limit of Quantification (BLQ) will be replaced with a value that is ½ of the lower limit of quantification (LLQ)
  - Results reported as < x will be treated in the same way as BLQ with LLQ=x
  - Otherwise SD and CI will not be calculated
  - Whenever meaningful, minimum, median and maximum will be presented based on the reported data (e.g. minimum = <10, median = 20, maximum = >100)

In summary tables of categorical variables, the number of non-missing observations by category will be presented with percentages. The number of missing observations will also be presented when non-zero. Unless otherwise specified, the denominator for each percentage will be the number of non-missing observations within the column. All percentages will be presented to one decimal place.

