## 10.4 MISSING DATA

For missing continuous variables, Last Observation Carried Forward (LOCF) imputation method will be used for both the OC Set and the NRI Set. Missing dichotomous variables will not be imputed in the OC Set but will be imputed in the NRI Set as non-responder.

There will be no other imputation of missing data in this study.

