### 11.3.1.6 Clinical remission, corticosteroid-free clinical remission and clinical response

**Clinical remission** is achieved when all the following criteria are met in the components of the Mayo Score:

- rectal bleeding sub-score = 0
- central or local endoscopy sub-score <= 1
- stool frequency sub-score <= 1.

**Corticosteroid-free clinical remission** is defined as clinical remission and concomitant corticosteroid free for  $\geq$  90 days prior to these timepoints among patients with clinical remission after 8 weeks of induction treatment (at baseline of ABX464-102 study).

**Clinical response** is defined as:

- reduction in Modified Mayo Score of at least 2 points and  $\geq$  30 percent from BIS
- with an accompanying decrease in rectal bleeding sub-score of  $\geq$  1 point or absolute rectal bleeding sub-score of  $\leq$  1 point.

Proportion of patients (n and percentage) will be presented for patients achieving clinical remission, corticosteroid-free clinical remission and clinical response at M12, M24, M36 and M48 (*Table 14.2.5.1 and 14.2.5.2*).

In addition, shift tables will be presented showing changes from BIS to each post baseline visit and from BOLS to each post baseline visit (*Table 14.2.5.3 and 14.2.5.4*) for clinical remission.

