| Modified Mayo Score        | n       | xx    | xx    | xx    |
|                            | Mean    | xx.xx | xx.xx | xx.xx |
|                            | SD      | xx.xx | xx.xx | xx.xx |
|                            | Median  | xx.xx | xx.xx | xx.xx |
|                            | Minimum | xx.x  | xx.x  | xx.x  |
|                            | Maximum | xx.x  | xx.x  | xx.x  |
| Faecal calprotectin (unit) | n       | xx    | xx    | xx    |
|                            | Mean    | xx.xx | xx.xx | xx.xx |
|                            | SD      | xx.xx | xx.xx | xx.xx |

|  |       |            |            |            |
|--|-------|------------|------------|------------|
| Median   | xx.xx | xx.xx      | xx.xx      |            |
| Minimum  | xx.x  | xx.x       | xx.x       |            |
| Maximum  | xx.x  | xx.x       | xx.x       |            |
| Number of subjects with concomitant Corticosteroid | N (%) | xx (xx.x%) | xx (xx.x%) | xx (xx.x%) |
| Clinical remission                                 | n     | xx         | xx         | xx         |
|  | Yes   | xx (xx.x%) | xx (xx.x%) | xx (xx.x%) |
|  | No    | xx (xx.x%) | xx (xx.x%) | xx (xx.x%) |
| Corticosteroid-free clinical remission             | n     | xx         | xx         | xx         |
|  | Yes   | xx (xx.x%) | xx (xx.x%) | xx (xx.x%) |
|  | No    | xx (xx.x%) | xx (xx.x%) | xx (xx.x%) |
| Clinical response                                  | n     | xx         | xx         | xx         |
|  | Yes   | xx (xx.x%) | xx (xx.x%) | xx (xx.x%) |
|  | No    | xx (xx.x%) | xx (xx.x%) | xx (xx.x%) |
| Endoscopic remission                               | n     | xx         | xx         | xx         |
|  | Yes   | xx (xx.x%) | xx (xx.x%) | xx (xx.x%) |
|  | No    | xx (xx.x%) | xx (xx.x%) | xx (xx.x%) |
| Endoscopic improvement                             | n     | xx         | xx         | xx         |
|  | Yes   | xx (xx.x%) | xx (xx.x%) | xx (xx.x%) |
|  | No    | xx (xx.x%) | xx (xx.x%) | xx (xx.x%) |

The denominator for each percentage is the number of non-missing observations within the column

Age was calculated using Year of Birth and date of first treatment and presented as age at last birthday.

BMI is the patient's body weight in kilograms divided by the square of the patient's height in meters.

\*The denominator is the total number of females within the column.

Source: Listing 16.2.4.1

Path\Filename

Page x/y

Version Date 20 MAY 2021

Template STATt004

Page 36 of 97

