## Clinical Response

Visit

n

xx

xx

xx

Etc

xx (xx.x%)

xx (xx.x%)

xx (xx.x%)

Etc

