## Clinical Response

Etc

The denominator for each percentage is the number of patients within the column.

Source: Listing 16.2.6.1

Path\Filename

*Programming Note: Please present subgroups in the following order:*

Version Date 20 MAY 2021

Template STATt004

Page 47 of 97

- *All patients*
- *Patients being in clinical response at Baseline Open-Label Study (BOLS)*
- *Patients not being in clinical response at Baseline Open-Label Study (BOLS)*
- *Patients previously treated with biological drugs*
- *Patients naive from biological drugs*

Page x/y

This layout also applies to:

*Table 14.2.5.2 Proportion of Patients: Clinical Remission, Corticosteroid-free Clinical Remission and Clinical Response (NRI Set)*

ABX464-102

ddMMMyyyy HH:MM

Table 14.2.5.3 Shift Table: Clinical Remission (OC Set)

<Subgroup>

|                           |            | 50mg ABX464 (101) +
50mg ABX464 (102)
(N=xx) | Placebo (101) +
50mg ABX464 (102)
(N=xx) | Total      |
|---------------------------|------------|--|--|------------|
| BIS                       | Yes        | xx (xx.x%)   | xx (xx.x%)                                     | xx (xx.x%) |
|                           | No         | xx (xx.x%)   | xx (xx.x%)                                     | xx (xx.x%) |
| BOLS                      | Yes        | xx (xx.x%)   | xx (xx.x%)                                     | xx (xx.x%) |
|                           | No         | xx (xx.x%)   | xx (xx.x%)                                     | xx (xx.x%) |
| Change from BIS to BOLS   | Yes -> Yes | xx (xx.x%)   | xx (xx.x%)                                     | xx (xx.x%) |
|                           | Yes -> No  | xx (xx.x%)   | xx (xx.x%)                                     | xx (xx.x%) |
|                           | Etc        |  |  |            |
| Visit                     | Yes        | xx (xx.x%)   | xx (xx.x%)                                     | xx (xx.x%) |
|                           | No         | xx (xx.x%)   | xx (xx.x%)                                     | xx (xx.x%) |
| Change from BIS to Visit  | Yes -> Yes | xx (xx.x%)   | xx (xx.x%)                                     | xx (xx.x%) |
|                           | Yes -> No  | xx (xx.x%)   | xx (xx.x%)                                     | xx (xx.x%) |
|                           | Etc        |  |  |            |
| Change from BOLS to Visit | Yes -> Yes | xx (xx.x%)   | xx (xx.x%)                                     | xx (xx.x%) |

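### Corticosteroid-free clinical remission is most naturally defined among patients in remission at the open-label baseline, but Tables 14.2.5.1/2 divide by all patients in the column

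*SAP*

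**What the plan says.** SAP 11.3.1.6 defines corticosteroid-free clinical remission as clinical remission with at least 90 days free of corticosteroids, "among patients with clinical remission after 8 weeks of induction treatment (at baseline of ABX464-102 study". Protocol 5.3.10 uses the same restriction with 12 weeks instead of 90 days. SAP 1.2 lists the change of interval and no change of population.

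The endpoint is to be shown as n and percentage at M12, M24, M36 and M48 in Table 14.2.5.1 (OC Set) and Table 14.2.5.2 (NRI Set). Both use one shell in SAP 15, whose footnote reads "The denominator for each percentage is the number of patients within the column". No exception is written for the corticosteroid-free rows.

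The fallback in SAP 10.1 is also not limited to BOLS remitters: "Unless otherwise specified, the denominator for each percentage will be the number of non-missing observations within the column". Elsewhere the SAP does write a denominator for a particular row; for childbearing status in Table 14.1.3 it says "The denominator is the total number of females within the column".

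The planned subgroup panels split by clinical response at BOLS and by prior biologics, not by remission at BOLS. For missing values, SAP 10.4 says "Missing dichotomous variables will not be imputed in the OC Set but will be imputed in the NRI Set as non-responder".

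**The concern.** A definition that restricts the endpoint to BOLS remitters calls for a proportion with BOLS remitters underneath. The shell puts everyone in the column underneath. Patients who were not in remission at BOLS then count as if they had failed an endpoint that does not apply to them, and the percentage falls short of 100% even if every BOLS remitter stays in steroid-free remission.

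The panel "Patients not being in clinical response at Baseline Open-Label Study (BOLS" shows this most clearly. Under assumptions set out in the working, it contains nobody to whom the endpoint applies, yet the shell would print 0.0% at every visit.

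At stake is how one secondary endpoint reads in the clinical study report. No test or decision depends on it.

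**Working it through.** The plan states no figure for this endpoint, so there is none to reproduce. The check compares x/N(column) with x/R, where x is the number in steroid-free remission at a visit and R is the number of BOLS remitters. Since x ≤ R, the printed rate is at most R/N(column).

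**Inputs (protocol 1.3).**
- Enrolled in ABX464-102: 22, of whom 15 had received ABX464 and 7 placebo.
- End of induction on ABX464: remission 35.0%, mucosal healing 50.0%, response 70.0%. With at most 23 patients, only n = 20 gives all three (7, 10 and 14).
- Remission on placebo: 11.1% = 1/9.

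**Range for R.** R is not in the documents. Assume that ABX464-101 used a comparable remission definition and that the 15 enrolled ABX464 patients come from those 20.
- Maximum: 7 + 1 = 8.
- Minimum: 7 − (20 − 15) = 2 from ABX464, and max(0, 1 − (9 − 7)) = 0 from placebo, so 2.

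**Ceiling on the printed rate, all-patients panel.**
- Total: 2/22 = 9.1% to 8/22 = 36.4%.
- Former ABX464 column: at most 7/15 = 46.7%.
- Former placebo column: at most 1/7 = 14.3%.
- Sensitivity: if remission in ABX464-101 was defined more strictly than in the SAP, mucosal healing gives a looser bound, R ≤ 10 + 1 = 11 and 11/22 = 50.0%. This takes mucosal healing to mean an endoscopy sub-score of 0 or 1, which the protocol does not state.

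**Example.** With R = 8 and x = 6, the definition gives 6/8 = 75.0% and the shell prints 6/22 = 27.3%.

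**Panel of non-responders at BOLS.** A remitter has rectal bleeding 0, stool frequency at most 1 and endoscopy at most 1, so a Modified Mayo Score of at most 2. From a score of 4 or more at the induction baseline, the fall is at least 2 points and at least (4 − 2)/4 = 50%, and bleeding is 0, so the SAP's response definition is always met. Enumerating sub-score patterns agrees: 0 of 176 remitter patterns fail for induction-baseline scores 4 to 9, and 10 of 40 fail for a score of 3. If all patients started at 4 or more and the same endoscopy reading serves both definitions, this panel holds no BOLS remitter. The entry criteria of ABX464-101 are not in the documents.

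**Non-responder imputation.** Under the present footnote it leaves the percentage unchanged, because missing patients are already in the denominator. It starts to matter once the denominator is corrected.

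**Can a reader rebuild the rate?** Largely. Table 14.1.3 gives the count in remission at Day 0, and Tables 14.2.5.3/4 give BOLS status and BOLS-to-visit shifts. This works only if the printed numerator is confined to BOLS remitters, and no programming note says so. At the M12 interim, 12 of 16 patients with an endoscopy were in remission, against R of at most about 8, so an unrestricted steroid-free count could include later remitters.

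**The case against.** The strongest objection is that the restriction sits inside the definition of the outcome and may be a condition of success: remission at the visit, steroid-free, and remission at BOLS, over all patients. Sustained clinical remission in SAP 11.3.1.8 works that way, and Tables 14.2.7.1/2 reuse a layout with the column denominator. The row-specific denominator for females could also suggest that silence here was deliberate. This reading is possible but less natural. Section 11.3.1.8 joins its two conditions in different words, whereas 11.3.1.6 says *among*. If the joint condition was meant, the SAP still needs to say so.

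A second objection stands and shapes the fix. Steroid-free remission is a subset of clinical remission and, on this definition, of sustained clinical remission. With column denominators the rows nest. If only one changes, 6/8 = 75% could appear beside, say, 7 sustained remitters printed as 7/22 = 32%, so the subset would look more common than the set that contains it.

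Two further complaints are tempting, and the documents do not support either.
- Table 14.1.3 shows the same endpoint at Day 0 with the rule "The denominator for each percentage is the number of non-missing observations within the column". A reader might infer that this too is wrong. But if the endpoint is undefined for non-remitters, they have no value, and the non-missing count may already equal the BOLS remitters.
- In the text available, the shell of Table 14.2.5.1 prints "Clinical Response" twice and has no corticosteroid-free heading. A reader might infer that the block was left out. The layout is visibly broken there, so this may be an extraction fault or a typing slip. The table title names the endpoint, and Listing 16.2.6.1 has a column for it.

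SAP 15 also allows layout changes and clarifying footnotes. That makes correction easy, but it does not say which denominator is meant.

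**Conclusion.** The point holds as a minor mismatch between a definition and a table footnote. The text alone establishes it, given the natural reading of *among*. The size does not come from the text: the ceiling of roughly 9% to 36% in the Total column depends on a remission definition in ABX464-101 comparable to the SAP's and on the inferred 7/20 and 1/9. The empty non-responder panel further needs induction-baseline scores of at least 4.

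A reader might go on to infer that the footnote hides later remitters, or that a 0.0% panel shows treatment failure. Neither follows. Patients who first remit after BOLS are excluded by the protocol's definition, not by the footnote. A zero in a panel with no eligible patients carries no information about treatment.

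Severity is minor because the counts are printed, the endpoint is secondary and descriptive, and the defined rate can largely be recovered from other planned tables.

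**What to change.** In the shared shell of Tables 14.2.5.1/2:

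1. Make sure the corticosteroid-free clinical remission block is labelled.
2. Give its rows their own footnote: the denominator is patients in clinical remission at BOLS, shown as n/N.
3. Code patients not in remission at BOLS as not applicable, so that non-responder imputation applies only to BOLS remitters. Print not applicable where a panel has no BOLS remitters.
4. Add a note that this conditional rate is not comparable with the all-patient rates for clinical remission and for sustained clinical remission (Tables 14.2.7.1/2), or also show the all-patient n/N so that the rows nest.

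For Table 14.1.3, just confirm that the non-missing count in this row means BOLS remitters.

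The cost is a heading check, a footnote, a note and a coding rule. It needs no new data and no protocol change, and should be done before database lock. The drawback is that the conditional rate rests on about 8 patients or fewer and sits beside rates with another denominator. Exact 95% intervals are 63% to 100% for 8/8 and 35% to 97% for 6/8, so the counts must be visible.

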5.3.9. Sigmoidoscopy

A Sigmoidoscopy will be performed in all subjects at Day 56/M2, Month 24, Month 36, and Month 48 (i.e. Study procedure).

In addition, monthly sigmoidoscopies could be performed if deemed necessary by the investigator (Until month 24). In such a case, the endoscopy rating will be reported in the eCRF (Total MCS).

Sigmoidoscopies procedures (or colonoscopies if applicable) at Month 24, Month 36, and Month 48 will be standardized for optimized video acquisition at clinical sites. Sigmoidoscopies should be performed according to the Central Imaging Management System Charter. Central Imaging Management System will be provided including a central image database. Once uploaded, video data will be analyzed for quality and resolution prior to independent review by an expert central reader. Study videos will be scored separately using the Mayo Clinic Score (excluding friability) for all time points by central readers.

The local reading result of sigmoidoscopy need to be available on M48 visit to check eligibility to enter study ABX464-108. The sigmoidoscopy can be performed within 14 days before the visit but not after the visit. If the sigmoidoscopy results (local reading) are not available on M48, the patient will be considered not eligible to enter the ABX464-108 study and will performed the end of study visit 28 days (+4 days) after M48.

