5.3.10. Clinical remission, clinical response, and corticosteroid-free clinical remission

The following remission and response will be assessed at M12, M24, M36 and M48:

Clinical remission is achieved when all the following criteria are met in the components of the Mayo Score:

- rectal bleeding sub-score = 0
- central endoscopy sub-score <= 1
- stool frequency sub-score <= 1.

Clinical response is defined as:

- reduction in Total Mayo Score of at least 2 points and >= 30 percent from baseline
- with an accompanying decrease in rectal bleeding sub-score of >= 1 point or absolute rectal bleeding sub-score of <= 1 point.

Corticosteroid-free clinical remission is defined as clinical remission at M12, M24, M36 and M48, and concomitant corticosteroid free for ≥ 12 weeks prior to these timepoints among patients with clinical remission after 8 weeks of induction treatment (at baseline of ABX464-102 study).

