|                           | Yes -> No  | xx (xx.x%)   | xx (xx.x%)                                     | xx (xx.x%) |
|                           | Etc        |  |  |            |
| Etc                       |            |  |  |            |

The denominator for each percentage is the number of non-missing observations within the column.

BIS: Day 0 of ABX464-101 study

---

BOLS: Day 56 of ABX464-101 study

---

Source: Listing 16.2.6.1

Path\Filename

Page x/y

*Programming Note: Please present subgroups in the following order:*

- All patients
- Patients being in clinical response at Baseline Open-Label Study (BOLS)
- Patients not being in clinical response at Baseline Open-Label Study (BOLS)
- Patients previously treated with biological drugs
- Patients naive from biological drugs

*This layout also applies to:*

*Table 14.2.5.4 Shift Table: Clinical Remission (NRI Set)*

ABX464-102

ddMMMyyyy HH:MM

Table 14.2.6.1 Proportion of Patients: Endoscopic Improvement and Endoscopic Remission (OC Set)

<Subgroup>

|  | 50mg ABX464 (101) +
50mg ABX464 (102)
(N=xx) | Placebo (101) +
50mg ABX464 (102)
(N=xx) | Total
(N=xx) |
|--|--|--|-----------------|
|--|--|--|-----------------|

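### The clinical remission shift tables are specified at every post-baseline visit, but remission needs an endoscopy that is mandatory at only 4 of 37, so literal non-responder imputation shows false loss of remission

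*SAP*

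**What the plan says.** **What remission requires.** SAP 11.3.1.6 makes it a composite of rectal bleeding, stool frequency and endoscopy. The endoscopic component is "central or local endoscopy sub-score <= 1".

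**When it is assessed.** Protocol 5.3.10: "The following remission and response will be assessed at M12, M24, M36 and M48". SAP 11.3.1.6 uses the same four time points for the remission proportions. For the shift tables it then says "In addition, shift tables will be presented showing changes from BIS to each post baseline visit and from BOLS to each post baseline visit".

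**When endoscopy is done.** Protocol 5.3.9: "A Sigmoidoscopy will be performed in all subjects at Day 56/M2, Month 24, Month 36, and Month 48". Further monthly endoscopies are allowed up to M24 at the investigator's discretion. M12 is not among the mandatory visits.

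**How missing values are handled.** Under SAP 10.4, missing dichotomous variables are left missing in the OC Set but "will be imputed in the NRI Set as non-responder"; SAP 6.2 gives the same rule. Both sections apply LOCF to missing continuous variables in both sets.

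**The denominator.** The shell for Table 14.2.5.3, whose layout also serves 14.2.5.4, carries the footnote "The denominator for each percentage is the number of non-missing observations within the column".

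**The concern.** At most visits remission cannot be scored for anyone, because no endoscopy is planned. Such a value is missing by design. It is not missing because a patient dropped out or skipped an assessment. The NRI rule does not separate the two cases, so a patient in stable remission is counted as a non-responder merely because nobody looked. In the shift from BOLS (the open-label baseline) this appears as Yes -> No.

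The long-term effect on clinical remission is a secondary objective, and these tables are the ones that lay out every transition, gains as well as losses. Followed literally, the NRI version would show remission disappearing at D7, reappearing at M2, disappearing again, and so on, in step with the endoscopy schedule and not with the disease.

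The OC version has a different problem. Patients without an endoscopy leave the denominator. Between mandatory endoscopies the percentages therefore describe only those patients the investigator decided to scope.

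**Working it through.** The documents state no visit count, so there is no figure to reproduce. The counts come from the flow chart (Protocol 5.1, repeated in SAP 16.1) and Protocol 5.2.

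**Post-baseline visits**
- D7, D14, D21, D28, D42, D56/M2: 6
- M3 to M24, monthly: 22
- M27 to M45, quarterly: 7
- M48: 1
- EoS: 1
- Total: 6 + 22 + 7 + 1 + 1 = 37

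Patients who enter ABX464-108 have no EoS visit, which leaves 36. (The visit list in SAP 3.4 omits M45. Counted that way, the total with EoS is also 36.)

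**Visits with a mandatory endoscopy:** M2, M24, M36, M48 = 4.

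**Visits with an optional endoscopy permitted.** Taking monthly until M24 to mean D28 and M3 to M23: 1 + 21 = 22.

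**Visits at which a patient in remission at BOLS, still attending and never relapsing, is tabulated Yes -> No in Table 14.2.5.4.** Here remission is treated as missing when there is no endoscopy, and then imputed:

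| Endoscopies done | Visits without one | Share |
|---|---|---|
| Mandatory only | 37 - 4 = 33 | 33/37 = 89% |
| Mandatory only, no EoS visit | 36 - 4 = 32 | 32/36 = 89% |
| Mandatory plus M12 | 37 - 5 = 32 | 32/37 = 86% |
| Mandatory plus all 22 optional | 37 - 26 = 11 | 11/37 = 30% |

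The 11 visits in the last row are D7, D14, D21, D42, M27, M30, M33, M39, M42, M45 and EoS. A patient who rolls over and has no EoS visit would, under the literal rule, still be scored No there.

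**Shifts from BIS.** Assuming that patients entering induction with active disease were not in remission at BIS, these rows read mostly No -> No. The false loss is confined to the BOLS rows.

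**The alternative order of operations.** If the endoscopy sub-score were carried forward by LOCF before remission was derived, lack of a scheduled endoscopy would force non-remission at 0 of 37 visits. The two orders therefore give 33 and 0 for the same patient with mandatory endoscopies only.

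**M12.** Protocol 1.3 reports that 16 of the 19 patients in the M12 per-protocol set had an endoscopy and 12 of the 16 were in remission: 12/16 = 75.0%. With all 22 enrolled patients in the denominator, no remission among the 22 - 16 = 6 without an M12 endoscopy, and the same remission calls, NRI gives 12/22 = 54.5%. Restricting the shift tables does not remove this M12 gap, so it has to be visible in the output.

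**The case against.** The strongest reply is that the artefact need not arise. The NRI Set also uses LOCF for continuous values, and the endoscopy sub-score is summarised with means and SDs (Tables 14.2.1.3 and 14.2.1.4). If it is carried forward first, remission is not missing. It is true that the SAP does not state the order of imputation and derivation. But it nowhere says that remission is built from a carried-forward sub-score, and SAP 10.4 treats dichotomous variables separately. Carrying the components forward would also leave NRI almost nothing to impute, even after dropout, so the OC and NRI remission tables would largely coincide. An M2 endoscopy could then stand for remission as late as M23. Two programmers could produce opposite tables, which is itself a reason to amend.

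A second reply is that SAP 11.3.1 ties efficacy summaries to measurement time points, that the Mayo score shell notes that TMS and MMS exist only where an endoscopy was done, and that SAP 15 allows layouts to change. None of this overrides the explicit instruction for the shift tables, whose shell has no such note. The rule in SAP 11.3 that borrows a nearby unscheduled endoscopy applies only when a scheduled one was not performed.

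A reader might infer more than the documents support:
- *That every patient loses remission at almost every visit.* The false loss concerns patients in remission at BOLS, at visits where they had no optional endoscopy.
- *That the OC table is selected towards flares.* Every M12 endoscopy, none of them mandatory under the current protocol, scored 0 or 1 (Protocol 1.3). The selection is by the investigator; its direction is unknown.
- *That durability is reported nowhere else.* Tables 14.2.7.1 and 14.2.7.2 report sustained remission at the four time points.
- *That about six patients are affected.* The induction rates in Protocol 1.3 give 0.350 x 15 + 0.111 x 7 = 6.0, but enrolment depended on patient willingness and investigator judgement. The number in remission at BOLS is not given.

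**Conclusion.** The defect stands. The shift tables are ordered at visits where remission cannot be scored by design, and the NRI rule as written converts those gaps into loss of remission. For a patient in remission at BOLS the false Yes -> No appears at 11 to 33 of 37 visits, depending on the optional endoscopies done; 32 is the figure for a patient with one at M12 and no other. This rests on the literal reading, in which remission is missing without an endoscopy and is then imputed. No count of affected patients can be derived from the documents.

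The reach is limited. The study is descriptive with a safety primary endpoint, and the remission proportions (Tables 14.2.5.1 and 14.2.5.2) and sustained remission do not have the every-visit artefact. It is worth correcting before database lock because the tables bear on a secondary objective, would mislead if followed, and are cheap to put right.

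**What to change.** 1. In SAP 11.3.1.6, for Tables 14.2.5.3 and 14.2.5.4, replace the instruction to cover all post-baseline visits with M2, M12, M24, M36 and M48.
2. Add a footnote to both tables that M12 had no mandatory endoscopy, with the number of patients scoped there.
3. In SAP 6.2 and 10.4, state that non-responder imputation applies only at time points where the endpoint is defined, and that for the shift tables these include M2.
4. In the same sections, state that remission is not derived from an endoscopy sub-score carried forward by LOCF.
5. Leave as-needed endoscopies at other visits in Listing 16.2.6.1, which already shows sub-scores and remission by visit.

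The cost is a few SAP sentences, one footnote and fewer table pages. No new data are needed and nothing is lost, because the listing keeps every optional score. Protocol section 9 already provides for documented SAP amendments before the final database lock.
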